5.10 Management of Hepatitis B Virus Reactivation

Primary antiviral prophylaxis is permitted as per local standard of care. Per protocol, HBV DNA testing by PCR is mandatory for subjects at risk for HBV reactivation see [Appendix A](#).

For subjects who are diagnosed with HBV reactivation while on treatment, study treatment should be interrupted until the infection is adequately controlled. If the benefits outweigh the risks, study treatment may be resumed with concomitant antiviral prophylaxis as per local standard of care. Consult a liver disease specialist as clinically indicated.

5.11 Contraception Requirements

Animal reproduction studies have not been conducted. Monoclonal antibodies such as daratumumab, are known to cross the placenta. Based on the mechanism of action, daratumumab may cause myeloid or lymphoid cell depletion and decreased bone density in the fetus. Therefore, female patients participating in this study should avoid becoming pregnant, and male patients should avoid impregnating a female partner.

Non-sterilized female patients of reproductive age and male patients should use effective methods of contraception.

5.12 Duration of Treatment and Patient Participation

Patients will be informed that they have the right to withdraw from the study at any time for any reason, without prejudice to their medical care. Patients will continue indefinitely unless the following occur:

- Lack of clinical benefit
- Patient's request to withdraw from the study or refusal of further therapy
- Unacceptable toxicity
- Pregnancy
- Physicians discretion
- Disease progression.
- Completion of up to 36 Cycles of study therapy

6.0 Evaluation During Study

6.1 Treatment and Event Schedule (see [Appendix A](#).)

6.2 Efficacy measurements

Patients will be staged once every 3 cycles +/- 7 days while on protocol. Efficacy evaluations will be based on changes in: myeloma protein measurements in serum and 24 hour urine; serum free light chain assay; bone marrow biopsy examination with NGF-based MRD testing at 6 months from the start of maintenance (+/- 2 weeks); as clinically indicated skeletal survey or other imaging as clinically indicated; and, extramedullary plasmacytoma evaluation as clinically indicated.

7.0 Statistical Considerations

7.1 Sample Size Justification

The primary endpoint of this study is progression-free survival (PFS). According to clinical trial [#NCT01998971 \(28\)](#), we expect that the median PFS without maintenance therapy is 12 months and the median PFS for the daratumumab-based maintenance therapy is expected to be 20 months. Given an accrual period of 36 months and a maximum follow-up time of 60 months, a sample size of 56 with the number of events of 42 will achieve the power of 0.91. The result is based on a two-sided test, a significance level of 0.05 with exponential assumption for survival time (29).

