1.0 Objectives

1.1 Primary Objective

To estimate the complete remission rate (CRR) by the International Myeloma Working Group (IMWG) criteria within 9 months post salvage auto-transplant with subcutaneous daratumumab and hyaluronidase-fihj plus pomalidomide maintenance therapy starting approximately 3 months post salvage auto-transplant in patients with relapsed myeloma.

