1.2 Secondary Objective

To evaluate progression-free survival (PFS).

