7.2 Futility and Toxicity Monitoring

The secondary endpoint is the complete remission rate (CRR). Remission will be evaluated 6 months after daratumumab and hyaluronidase-fihj plus pomalidomide maintenance therapy (approximately 9 months post ASCT). Complete remission is defined as achieving a negative immunofixation of serum and urine, disappearance of any soft tissue plasmacytomas, and < 5% plasma cells in bone marrow. In patients for whom only measurable disease is by serum FLC level, normal FLC ratio of 0.26 to 1.65 in addition to CR criteria is required. The futility and toxicity will be monitored during the study.

We desire that the CRR is at least 10% and the dose-limiting toxicity rate is no higher than 33%. Toxicity is defined as treatment-related unmanageable toxicities, including grade 3 non-hematologic effects or grade 4 hematologic effects, that require delay or termination of the treatment during cycle one. Futility and toxicity will be monitored by the Bayesian stopping boundaries calculated on the basis of beta-binomial distributions using the method of Thall, Simon, and Estey (30). Independence is assumed between CR and toxicity. Patients will be monitored in cohorts of size (8).

We will enroll a minimum of 16 patients before stopping. The following stopping rules and boundaries were developed using the Multc Lean application (version

2.1) from the MDACC Biostatistics department. The stopping rules are as follows:

$$\Pr [\theta_E < 0.10 | \text{data}] > 0.90$$

$$\Pr [T_E > 0.33 | \text{data}] > 0.95$$

Enrollment will be stopped early if there is > 90% probability that the CRR is < 10% or there is > 95% probability that the toxicity rate is higher than 33%. The notation θ_E denotes the marginal remission rate, assuming that θ_E follows a prior distribution of beta (0.2, 1.8). T_E denotes the toxicity rate, assuming that T_E has a prior distribution of beta (0.66, 1.34). The corresponding stopping boundaries for futility monitoring are as follows: enrollment will be stopped early due to futility if (# of patients with remission) / (# patients evaluated) \leq 0/16-24, 1/32, 2/40-48, or 3/56.

Stopping boundaries corresponding to this probability criterion for toxicity will terminate the trial if (# of patients with toxicity) / (# patients evaluated) \geq 9/16, 13/24, 16/32, 19/40, 22/48, or 25/56.

We will suspend accrual while waiting to assess patient outcomes.

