7.3 Analysis Plan

Patients' demographic, clinical characteristics, and safety data will be summarized using descriptive statistics such as mean, standard deviation, median, interquartile range, and frequency where appropriate.

Progression-free survival is defined as the interval from the date of initiation of maintenance therapy after salvage ASCT to the earlier of the first documentation of objective disease progression or death from any cause. Disease progression will be assessed using myeloma protein measurements in serum and 24 hour urine; serum free light chain assay; bone marrow biopsy examination with MGF-based MRD testing at 6 months (+/- 2 weeks) from the start of maintenance, and then yearly as indicated; skeletal survey or other imaging as clinically indicated; and, extramedullary plasmacytoma evaluation as clinically indicated. Progression is defined by the IMWG as a 25% increase from the lowest response value in any of the following: a) serum M protein with absolute increase ≥ 0.5 g/dL, b) urine M protein with absolute increase of at least 200 mg/24 hour, c) difference between involved and uninvolved FLC levels with absolute increase of at least 10 mg/dL (in patients without measurable serum or urine M protein), d) bone marrow plasma cell percentage with absolute percentage of at least 10% (in patients without measurable serum or urine M protein or FLC levels), e) new or definite increase in size of existing bone lesions or soft tissue plasmacytoma, f) development of hypercalcemia that can be attributed solely to myeloma. Data from surviving, non-progressing patients will be censored at the last time of follow-up. Progression-free survival will be summarized descriptively using the Kaplan-Meier method (including the median, 95% confidence interval, and survival curve). The proportion of patients alive and without disease progression at 6 months of daratumumab and hyaluronidase-fihj plus pomalidomide maintenance therapy will be summarized. The estimate will be accompanied by a two-sided exact 95% binomial confidence interval. In addition, a Cox regression analysis may be performed if demographic and clinical factors potentially affecting PFS are identified.

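### Sections 1.1–1.2 make complete remission rate (CRR) primary and PFS secondary, Sections 7.1–7.2 reverse this, and the PFS test behind the 0.91 power is missing from Section 7.3

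*Combined protocol and SAP*

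**What the plan says.** The objectives and the statistical section rank the same two endpoints in opposite order.

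- Section 1.1, primary objective: "To estimate the complete remission rate (CRR) by the International Myeloma Working Group (IMWG) criteria within 9 months post salvage auto-transplant".
- Section 1.2, secondary objective: "To evaluate progression-free survival (PFS".
- Section 7.1: "The primary endpoint of this study is progression-free survival (PFS".
- Section 7.2: "The secondary endpoint is the complete remission rate (CRR".

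Section 7.1 sizes the trial on PFS, with a median of 12 months without maintenance and 20 months expected with it, 36 months of accrual and at most 60 months of follow-up. It concludes that "a sample size of 56 with the number of events of 42 will achieve the power of 0.91" and adds: "The result is based on a two-sided test, a significance level of 0.05 with exponential assumption for survival time". It does not name the test statistic.

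Section 7.3 then says: "Progression-free survival will be summarized descriptively using the Kaplan-Meier method". It adds the proportion progression-free at 6 months with an exact interval, and an optional Cox model for patient factors. For CRR it plans an estimate with a 95% credible interval. Section 7.2 gives CRR a futility rule built on a 10% threshold and a beta(0.2, 1.8) prior. Appendix A, footnote i, mentions a primary PFS analysis in passing.

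**The concern.** The primary endpoint fixes which result the trial is judged on. Here a reader can cite protocol text for either one, so the headline could be chosen after the data are seen. The two rankings also imply different kinds of conclusion: Section 1.1 asks for an estimate of CRR, while Section 7.1 relies on a hypothesis test of PFS.

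The analysis plan does not settle the matter. If PFS is primary, the test that carries the power is absent from Section 7.3, and so is any rule for declaring that 12 months has been exceeded. If CRR is primary, the justification of 56 patients in Section 7.1 belongs to the secondary endpoint, and the plan does not say how precisely 56 patients would estimate CRR.

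**Working it through.** **1. Labels side by side**

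| Endpoint | Sections 1.1–1.2 | Sections 7.1–7.2 |
|---|---|---|
| CRR | primary | secondary |
| PFS | secondary | primary |

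**2. Reproducing Section 7.1**

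Inputs from Section 7.1: medians 12 and 20 months, accrual 36 months, maximum follow-up 60 months, N = 56, 42 events, two-sided 0.05, exponential times. Assumptions added here: uniform accrual, analysis at month 60 of the study, no dropout.

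- Hazard at a 20-month median: λ = ln 2 / 20 = 0.03466 per month.
- P(event by month 60) = 1 − [exp(−24λ) − exp(−60λ)] / (36λ) = 1 − (0.4353 − 0.1250) / 1.2477 = 0.7513.
- Expected events: 56 × 0.7513 = 42.07 (stated: 42).
- Power, one-sample test on the log hazard: Φ(√42 × ln(20/12) − 1.96) = Φ(3.311 − 1.960) = 0.912 (stated: 0.91).
- Power, exact chi-square form at 42 events (84 degrees of freedom): 0.917.

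Other readings do not fit. A one-sided 0.05 test gives 0.952. Sixty months of follow-up after accrual ends gives 52.0 events. A two-arm comparison with 42 events gives 0.38. Section 7.1 therefore describes a one-sample exponential test against 12 months, and its arithmetic is sound.

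**3. What that test would require**

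At 42 events, the smallest estimated median that rejects 12 months is:

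- log-hazard form: 12 × exp(1.96/√42) = 16.24 months;
- exact form: 12 × χ²(0.975; 84) / 84 = 12 × 111.24 / 84 = 15.89 months.

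These limits apply to the exponential maximum-likelihood median (total time at risk × ln 2 / events). They do not apply to the Kaplan-Meier median that Section 7.3 reports.

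**4. Does the Kaplan-Meier summary stand in for the test?**

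Suppose success were read as the lower 95% limit of the Kaplan-Meier median (log-log interval) lying above 12 months. In 10,000 simulated trials with a true median of 20 months, this happened in about 0.65. The log-hazard exponential test rejected in 0.918 of the same trials. The stated 0.91 therefore does not carry over to the Section 7.3 summary.

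**5. Timing**

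Section 7.1 sets no event trigger; 42 is the expected count at month 60. With events by then binomial(56, 0.7513), P(fewer than 42) = 0.42. At a true median of 24 months, the event probability is 0.6891 and P(fewer than 42) = 0.80. By simulation, the log-hazard test done at month 60, whatever the event count, keeps power at about 0.92 and two-sided type I error at about 0.05.

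**6. CRR precision with 56 evaluable patients**

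The posterior is beta(0.2 + x, 1.8 + 56 − x), using the Section 7.2 prior, with an equal-tailed 95% interval. The counts are illustrative.

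| Remissions | Rate | 95% credible interval | Half-width (points) |
|---|---|---|---|
| 6/56 | 10.7% | 4.2–19.7% | 7.8 |
| 11/56 | 19.6% | 10.3–30.3% | 10.0 |
| 16/56 | 28.6% | 17.3–40.0% | 11.4 |
| 22/56 | 39.3% | 26.3–51.0% | 12.4 |

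**The case against.** The best defence is that the plan is workable despite the labels. The PFS arithmetic is right, Section 7.1 does mention a two-sided test, PFS has a planned interval, and CRR has an estimate, a prior and a futility rule. An objective worded as estimation does not strictly need a power calculation. All of this stands, and it limits the point to the ranking and the missing test. It does not say which result decides the trial, and it does not put a test against 12 months into Section 7.3.

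Several stronger readings are tempting but not supported:

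- **That the sample size is wrong.** It reproduces. The fault is that the test it assumes is not in the analysis plan.
- **That footnote i settles the ranking in favour of PFS.** Its phrase can simply mean the main analysis of PFS, whatever that endpoint's rank.
- **That 28% is a CRR benchmark on which the endpoints could conflict.** Section 2.1 reports that figure for a different regimen. The only CRR threshold set in the plan is in Section 7.2: "We desire that the CRR is at least 10% and the dose-limiting toxicity rate is no higher than 33" percent.
- **That no prior exists for the CRR interval.** Section 7.2 gives one for the remission rate. Section 7.3 does not repeat it, but carrying it forward is the natural reading and only needs confirming.
- **That the PFS analysis must wait for 42 events.** Section 7.1 sets no such trigger.

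**Conclusion.** The point holds, and it must be fixed before outcome data are analysed. The primary and secondary labels are reversed between Sections 1.1–1.2 and 7.1–7.2, and the documents do not show which order was intended. Under either order the plan is incomplete. With PFS primary, the 0.91 power belongs to a test that Section 7.3 never specifies, and the Kaplan-Meier limit used in its place would have power of about 0.65. With CRR primary, the size of 56 is argued only from PFS, and the resulting half-width of about 8 to 12 points is not stated.

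The PFS figures rest on exponential times, uniform accrual, analysis at month 60, no dropout and all 56 patients enrolled. Early stopping under Section 7.2 was not built into them. The CRR widths rest on 56 evaluable patients and the Section 7.2 prior. It would go too far to infer that the trial is too small or that a ranking has already been chosen from the data; nothing in the documents shows either.

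**What to change.** Choose one ranking and apply it in Sections 1.1, 1.2, 7.1, 7.2 and 7.3 and, for consistency, in Appendix A footnote i. The choice is the sponsor's.

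- **If PFS is primary:** swap Sections 1.1 and 1.2. Add to Section 7.3 a two-sided 0.05 one-sample exponential test of median PFS against 12 months, naming the statistic and the analysis time. The log-hazard test at the planned 60 months needs no extra follow-up. A 42-event trigger is possible, but may run past month 60 (about a 42% chance at a 20-month median). Keep the Kaplan-Meier median as the descriptive summary, and state that the test's critical value refers to the exponential median.
- **If CRR is primary:** correct the labels in Sections 7.1 and 7.2. Say that the 0.91 power belongs to the secondary PFS endpoint, and specify its test if that power is to be relied on. State the precision that 56 evaluable patients give, and confirm that the credible interval uses the beta(0.2, 1.8) prior.

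Cost: a wording amendment with no extra patients. No extra follow-up is needed if the PFS analysis stays at month 60; an event-driven analysis could need more.

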7.2 Futility and Toxicity Monitoring

The secondary endpoint is the complete remission rate (CRR). Remission will be evaluated 6 months after daratumumab and hyaluronidase-fihj plus pomalidomide maintenance therapy (approximately 9 months post ASCT). Complete remission is defined as achieving a negative immunofixation of serum and urine, disappearance of any soft tissue plasmacytomas, and < 5% plasma cells in bone marrow. In patients for whom only measurable disease is by serum FLC level, normal FLC ratio of 0.26 to 1.65 in addition to CR criteria is required. The futility and toxicity will be monitored during the study.

We desire that the CRR is at least 10% and the dose-limiting toxicity rate is no higher than 33%. Toxicity is defined as treatment-related unmanageable toxicities, including grade 3 non-hematologic effects or grade 4 hematologic effects, that require delay or termination of the treatment during cycle one. Futility and toxicity will be monitored by the Bayesian stopping boundaries calculated on the basis of beta-binomial distributions using the method of Thall, Simon, and Estey (30). Independence is assumed between CR and toxicity. Patients will be monitored in cohorts of size (8).

We will enroll a minimum of 16 patients before stopping. The following stopping rules and boundaries were developed using the Multc Lean application (version

2.1) from the MDACC Biostatistics department. The stopping rules are as follows:

$$\Pr [\theta_E < 0.10 | \text{data}] > 0.90$$

$$\Pr [T_E > 0.33 | \text{data}] > 0.95$$

Enrollment will be stopped early if there is > 90% probability that the CRR is < 10% or there is > 95% probability that the toxicity rate is higher than 33%. The notation θ_E denotes the marginal remission rate, assuming that θ_E follows a prior distribution of beta (0.2, 1.8). T_E denotes the toxicity rate, assuming that T_E has a prior distribution of beta (0.66, 1.34). The corresponding stopping boundaries for futility monitoring are as follows: enrollment will be stopped early due to futility if (# of patients with remission) / (# patients evaluated) \leq 0/16-24, 1/32, 2/40-48, or 3/56.

Stopping boundaries corresponding to this probability criterion for toxicity will terminate the trial if (# of patients with toxicity) / (# patients evaluated) \geq 9/16, 13/24, 16/32, 19/40, 22/48, or 25/56.

We will suspend accrual while waiting to assess patient outcomes.

The operating characteristics of these rules are shown in the table below.

	True Pr(Response)	True Pr (Tox)	Pr (Stop Early)	Average # treated
1	10%	15%	0.32	46.0
2	10%	33%	0.38	44.0
3	10%	40%	0.55	39.1
4	20%	25%	0.04	54.4
5	20%	33%	0.13	52.0
6	20%	40%	0.36	45.6
7	25%	20%	0.013	55.5
8	25%	33%	0.10	52.8
9	25%	40%	0.35	46.2
10	30%	20%	0.005	55.8
11	30%	33%	0.10	53.1
12	30%	45%	0.60	39.0
13	40%	20%	0.002	55.9
14	40%	33%	0.09	53.2
15	40%	45%	0.60	39.1

The dataset for efficacy will be based on evaluable patients while the dataset for safety includes all patients who receive the maintenance therapy and will be

evaluated as intention to treat (ITT). Based on the toxicity profile of daratumumab, we do not expect to have patients who receive fewer than 2 cycles due to AE's.

Patient who received < 2 cycles due to AEs will be inevaluable for efficacy (response). All the other analysis will be conducted using intention to treat dataset.

